2.2. Study Objectives

2.2.1. Primary Objective

The primary objective of this study is to assess the safety and tolerability of ataluren in male children with nmDMD aged ≥ 6 months to < 2 years old.

2.2.2. Secondary Objectives

The secondary objective of this study is to assess the PK of ataluren in male children with nmDMD aged ≥ 6 months to < 2 years old.

2.2.3. Exploratory Objectives

The exploratory objective of this study is to assess changes from baseline in creatine kinase (CK) levels.

2.3. Study Endpoints

2.3.1. Primary Endpoint

The primary endpoint of this study is the overall safety profile of ataluren in terms of type,

frequency, severity, seriousness, timing, and relationship to study therapy of any TEAE during the 24 weeks of treatment.

2.3.2. Secondary Endpoints

The secondary endpoint of this study is the evaluation of PK parameters after 24 weeks of treatment as follows:

- AUC0-24 and AUC0-6
- T_{max}
- C_{max}
- Ctrough

2.3.3. Exploratory Endpoints

Changes from baseline in CK levels after 24 weeks of treatment

2.4. Sample Size

Sample size is not based on any formal statistical hypothesis for this study. It is anticipated that up to 10 subjects (minimum of 6 subjects) will be enrolled.

2.5. Randomization

Not applicable for this study.

2.6. Blinding

Not applicable for this study.

2.7. Study Assessments

2.7.1. Physical Examination

A full physical examination (including evaluation of cardiovascular system, chest and lungs, thyroid, abdomen, nervous system, skin and mucosae, musculoskeletal system, eyes, ears, nose, mouth, throat, spine, lymph nodes, and extremities) will be conducted at Screening (Visit 1), Week 0 (Baseline/Visit 2), Week 4 (Visit 3), Week 12 (Visit 4), and Week 24 (Visit 5-EOT/Early Termination).

2.7.2. Laboratory Assessment

Hematology, biochemistry, and urinalysis laboratory assessment will be analyzed by the local laboratory at the investigative site. These parameters will be collected at Screening (Visit 1), Week 0 (Visit 2/Baseline), Week 4 (Visit 3), Week 12 (Visit 4), and Week 24 (Visit 5 - EOT/Early Termination).

2.7.3. Confirmation Gene Sequencing

A blood sample for dystrophin gene sequencing to confirm the presence of a nonsense mutation will be drawn at screening (Visit 1).

2.7.4. Pharmacokinetic Assessment

The PK parameters will be evaluated based on frequent blood sampling During PK assessments at baseline (Visit 2) Week 4 (Visit 3), and EOT at Week 24 (Visit 5), subjects will remain in the clinic until all blood draws are complete. At each assessment period, blood sampling will occur immediately pre-dose, and at 1-, 2-, 3-, and 4-hours post-dose following the morning and midday doses and immediately pre-dose and at 1, 2, 3, 4 and 12 (before the next day morning dose) hours post-dose following the evening ataluren dose. The PK parameters, including AUC0-24 (following the morning ataluren dose), AUC0-tau (AUC0-6 following the morning and mid-day ataluren doses and AUC0-12 following the evening ataluren doses), Tmax, Cmax, and Ctrough after each dose will be assessed.

The blood/plasma partition sampling will occur at 2.5 hour and 4.5 hour post morning dose at baseline (Visit 2), Week 4 (Visit 3), and EOT at Week 24 (Visit 5).

2.7.5. Height, Weight, and Body Mass Index

Height (in cm), weight (in kg) and body mass index (BMI) (kg/m²) will be measured at all study visits.

2.7.6. Vital Signs

Vital signs (heart rate and systolic and diastolic blood pressure [BP]) will be monitored at all protocol -required study visits. Heart rate and BP determinations will be performed with the subject in a supine position after a 5-minute rest.

2.7.7. Electrocardiogram

A 12-lead ECG will be obtained at screening (Visit 1), baseline (Visit 2), Week 4 (Visit 3), and EOT at Week 24(Visit 5). The ECGs will be read locally at investigational sites and interpreted for clinical significance. The findings will be captured in source documents and within the eCRF.

2.7.8. Adverse Events

An Adverse Event (AE) is any untoward medical occurrence associated with the use of a drug in humans, whether or not it is considered related to the drug.

All AEs (both serious and nonserious) that occur in subjects during the AE reporting period must be recorded. All AEs are to be recorded in the source documents and on the eCRF using concise

medical terminology; whenever possible terms contained in Medical Dictionary for Regulatory Activities (MedDRA) should be employed.

2.7.9. Concomitant Medications

Concomitant medication information will be collected and documented at each scheduled clinic visit, from screening (Visit 1) through EOT at Week 24 (Visit 5) and at the post-treatment follow-up visit (if applicable).

3. STUDY POPULATIONS

3.1. Safety Population

The safety population will include all subjects who receive at least one dose of ataluren and will be used for all safety analyses.

3.2. PK Population

The PK population will include all subjects who receive at least one dose of ataluren and have one PK concentration datum. The PK population will be used for all PK analyses.

4. GENERAL CONSIDERATIONS

4.1. Tables, Figures, and Listings

Summary statistics for continuous variables will include n (number of subjects), mean, median, minimum, and maximum. For PK analysis, n, mean, SD, coefficient of variation (CV), geometric mean, and geometric mean CV will also be provided for PK population only. Summary statistics for categorical variables will include N (number of subjects in population), n (number of subjects in category), % (percent of subjects in category). Where applicable, the summary data will also be provided in graphical presentation.

By-subject data listings will be created for each eCRF domain sorted by treatment, subject, and associated dates, where applicable.

4.2. Baseline and Endpoint Definitions

The study baseline, defined as the last assessment prior to the first dose of ataluren, will be used for analyzing and summarizing safety endpoints.

4.3. Interim Analyses

There is no interim analysis planned for this study.

4.4. Missing Data Handling

No missing value imputation will be applied to this study.

4.5. Analysis Visits

All data analyses for this study will be performed based on nominal visits collected on the eCRF.

5. SUBJECT DATA

All subject data described in this section will be summarized based on safety population. Additional summaries will be provided based on PK population if PK population is different from the safety population in demographic tables.

5.1. Subject Disposition and Study Populations

The number of subjects in each analysis population will be summarized using frequency count. The number of subjects who completed or discontinued from the study and the reasons of discontinuation will be summarized based the safety population. Reasons for screening failures and early discontinuations, and time of withdrawal from study will also be summarized.

5.2. Duration of Treatment with Study Drug

Duration of treatment with study drug during study will be calculated as:

Duration (days) = Date of last dose of study drug - Date of first dose of study drug + 1

Duration of treatment with study drug in days will be presented in by-subject listing only on safety population.

5.3. Treatment Administration and Drug Compliance

Study drug administration information including study drug start and end dates, dose interruptions start and stop dates, and reasons for dose interruption or dose deviations will be presented in a by-subject listing based on safety population.

5.4. Demographic and Baseline Characteristics

Demographic and baseline characteristics including age (in month), gender, race, ethnicity, height, weight, and BMI will be summarized for safety population.

5.5. Disease Characteristics

Disease characteristics including prior dystrophin gene sequencing, location of nonsense point mutation, and stop codon type will be provided in the by-subject listings only. Age at diagnosis of dystrophinopathy, signs/symptoms/laboratory results used to support diagnosis will be listed as well.

5.6. Medical History

Medical history will be presented in the by-subject listing for safety population.

5.7. Concomitant Medications and Non-Drug Treatments

Concomitant medications and non-drug treatments will be coded using the World Health Organization Drug Dictionary (WHODD), version March 2023 or higher.

Prior medications and non-drug treatments are defined as those taken any time prior to the first dose of ataluren (Week 0). Concomitant medications and non-drug treatments are defined as those taken any time during the study treatment period (the first dose date of Ataluren through the last follow-up date within study).

The use of concomitant medications and non-drug treatments will be listed.

V1.0

6. **EFFICACY EVALUATION**

No functional assessments will be captured for this study. The change from baseline in the CK levels will be considered as an exploratory efficacy endpoint for this study.

6.1. Primary Analysis

Not applicable to this study.

6.2. Exploratory Endpoints

Summary tables on change from baseline in CK levels by visits will be provided.

7. ATALUREN CONCENTRATIONS AND PHARMACOKINETIC PARAMETERS

7.1. Descriptive Analysis

Descriptive statistics (n, mean, SD, CV%, Geo mean, Geo CV%, median, min, and max) will be used to summarize the blood and plasma ataluren concentrations at each timepoint and PK parameters by cycle, day, and dose interval at 2.5 hour and 4.5 hour post morning ataluren dose at each visit.

7.2. Blood and Plasma Concentrations

Blood and plasma concentration values below the quantitation limit (BQL) of the bioanalytical assays were treated as zero for the descriptive statistics. Individual values that were BQL were presented as BQL in the concentration data listing. For the presentation of summary and order statistics, if at least 1 subject had a concentration value BQL for the given timepoint, then the minimum value was displayed as BQL. If over 50% of the subjects at a given timepoint have values BQL then the descriptive statistics will not be presented and will instead display as '<LLOQ' for the mean and missing for all other statistics. Concentration values that were BQL were BQL were considered missing for any ratio or natural log transformed statistical analyses.

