7.3. Blood Pharmacokinetic Parameters

Blood PK parameters for ataluren will be estimated using non-compartmental methods with WinNonlin®. Any data points designated as anomalous values that would impact PK should be predefined before database lock if possible and identified in the report with a rationale for exclusion. The PK parameters will be estimated from the concentration-time profiles, and AUCs will be calculated using the Linear-Log Trapezoidal method (equivalent to the linear up / log down option in WinNonlin). For the estimation of PK parameters, BQL concentration following first dose at pre-dose and up to the first measurable concentration will be set to zero, BQL concentration will be set to missing otherwise. Actual sampling times, rather than scheduled sampling times, will be used in all computations involving sampling times. Actual dose will be used to calculate dose-dependent parameters. Parameters will be summarized by dose (morning, mid-day, evening) and entire day, and visits (baseline, Week 4, and EOT at Week 24). AUC0-tau and AUC0-inf for a subject at any specific dose interval will be reported as NR (not reportable) if there is one sample missing during the dose interval, and consequently the AUC0-24 for the subject at the specified day will be reported as NR.

The following blood PK parameters will be determined using non-compartmental methods as appropriate, for each visit:

Parameter	Description	Dose
C _{max}	Maximum blood concentration; determined directly from the concentration time profile; if the maximum blood concentration occurs at more than one time point, C _{max} is defined as the first maximum value	Morning, Mid- day, Evening
T _{max}	Time to C_{max} ; if the maximum value occurs at more than one time point, T_{max} is defined as the first time point with this value.	Morning, Mid- day, Evening
Ctrough	Trough blood concentration; measured blood concentration at the end of the dosing interval, directly before next administration.	Morning,

Parameter	Description	Dose
AUC ₀₋₂₄	Area under the blood concentration vs time curve (AUC) from time 0 to 24 hours post first morning dose.	Morning
AUC _{0-т}	AUC from time 0 to 6 hours post-dose following the morning and mid-day ataluren doses and AUC from time 0 to 12 hours post- dose following the evening ataluren doses. AUC from time 0 to 6 hours post-dose following the evening ataluren dose will also be calculated.	Morning, Mid- day, Evening

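### Setting late BQL values to missing drops undetectable troughs from the Ctrough summary and biases it upward; in the concentration tables the two means rest on different children under one n

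*SAP*

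**What the plan says.** **Concentration tables.** SAP 7.1 lists "Descriptive statistics (n, mean, SD, CV%, Geo mean, Geo CV%, median, min, and max", among other uses for blood and plasma concentrations at each time point. It gives one n for the whole set. SAP 7.2 says that BQL values "were treated as zero for the descriptive statistics" but are "considered missing for any ratio or natural log transformed statistical analyses". Two display rules limit what can be hidden. If any child is BQL, "then the minimum value was displayed as BQL". And "If over 50% of the subjects at a given timepoint have values BQL then the descriptive statistics will not be presented".

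**PK parameters.** SAP 7.3 has a split rule. A "BQL concentration following first dose at pre-dose and up to the first measurable concentration will be set to zero"; after that, "BQL concentration will be set to missing otherwise". The same section defines Ctrough as the "measured blood concentration at the end of the dosing interval, directly before next administration". SAP 2.1 and 2.7.4 ask for Ctrough after each dose.

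**Protocol.** Sections 2.2.2 and 8.5.4 define Ctrough as the level before the morning dose and make it a secondary endpoint. Each profile has an opening sample before the morning dose and a closing sample 12 hours after the evening dose, taken before the next morning dose. SAP 9 declares no change from the protocol's planned analyses.

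**The concern.** There are two separate problems.

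1. **Ctrough.** The sample 12 hours after the evening dose normally follows measurable concentrations. If it is BQL, SAP 7.3 makes it missing. Under the SAP definition that sample is the evening-dose trough, so the child with the lowest value is the one who leaves the summary. The samples before the mid-day and evening doses, which are the troughs of the two preceding doses, face the same rule. What remains is biased upward.

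2. **Concentration tables.** A geometric mean cannot usefully be formed with a zero in the data, so the missing rule is its only workable reading. The arithmetic mean then covers every child and the geometric mean only those with quantifiable drug, while the table shows one n. A reader cannot see the difference and may find a geometric mean larger than the arithmetic mean, which is impossible for one set of values.

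Protocol 8.5.4 says the PK results will be set against earlier studies. Protocol 3.2 says comparable pharmacokinetics helped to support the extension to ages 2 to under 5 years. A trough summary that silently omits undetectable values weakens that comparison. With 6 to 10 children, one BQL value is 10 to 17% of the data.

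**Working it through.** The plan states no figure to reproduce: it has no formal hypothesis, no quantitation limit and no expected BQL rate.

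**Step 1. Which rule a BQL trough meets (SAP 7.3)**

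- Sample 12 hours after the evening dose: it follows measurable concentrations, so BQL becomes missing and the child leaves the Ctrough summary.
- Opening pre-morning sample, with the rule's first dose read as the first dose of the profile day: BQL becomes zero and stays in the arithmetic summary, though it cannot enter the geometric mean.
- Opening pre-morning sample, with the first dose read as the first dose ever: handling at Weeks 4 and 24 is unclear.
- At baseline the opening sample precedes all drug, so only the later samples can be on-treatment troughs.

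Both the opening and the closing sample precede a morning dose, so the protocol wording alone does not settle the choice.

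**Step 2. Size of the Ctrough bias where BQL is missing**

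Assume lognormal troughs with log SD s, a share f that is BQL, and z = Φ⁻¹(f). The arithmetic mean of detectable values divided by the true mean is Φ(s − z)/(1 − f). For the geometric mean the ratio is exp[s·φ(z)/(1 − f)]. All s and f are assumptions.

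| f | s | Arithmetic ratio | Geometric ratio |
|---|---|---|---|
| 10% (z = −1.282) | 0.5 | 0.963/0.9 = 1.07 | 1.10 |
| 10% | 1.0 | 0.989/0.9 = 1.10 | 1.22 |
| 30% (z = −0.524) | 0.5 | 0.847/0.7 = 1.21 | 1.28 |
| 30% | 1.0 | 0.936/0.7 = 1.34 | 1.64 |

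The numerators, Φ(s − z), are also the ratios obtained if BQL is kept as zero. That mean is too low by 1 to 4% at 10% BQL and by 6 to 15% at 30%. In each row this is a smaller error than dropping the values.

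**Step 3. Concentration tables: when the geometric mean exceeds the arithmetic mean**

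With b of n values BQL and f = b/n, the printed arithmetic mean is (1 − f) × AM of the quantifiable values. The printed geometric mean is the GM of the quantifiable values. If those are lognormal, AM/GM = √(1 + CV²), so the order reverses when CV < √(1/(1 − f)² − 1).

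- n = 6, b = 1: √(1/0.8333² − 1) = √0.44 = 66%.
- n = 10, b = 1: √(1/0.9² − 1) = √0.2346 = 48%.

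The suppression rule still lets 3 of 6 or 5 of 10 BQL be shown.

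*Illustration* (assumed limit 0.5, arbitrary units): one BQL value plus 0.6, 0.9, 1.2, 1.8 and 2.5 (CV 54%). The arithmetic mean is 7.0/6 = 1.167 on 6 children. The geometric mean is 2.916^(1/5) = 1.239 on 5 children.

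*Simulation* (200,000 replicates per setting, lognormal, assumed CV 40 to 100% and BQL probability 10 to 30%): given between 1 and n/2 BQL values, the reversal occurred in 65% to about 100% of tables for n = 6, and in 34% to about 100% for n = 10.

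**The case against.** The strongest reply has five parts.

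- **BQL is not simply missing for PK parameters.** This stands. Leading values are set to zero, and on one reading of the protocol's Ctrough an undetectable trough stays in the arithmetic mean. The loss is firm only under the SAP's end-of-interval definition.
- **The two mechanisms must not be merged.** This stands. A reader might infer that the printed geometric mean of Ctrough can exceed its arithmetic mean. Where a BQL trough is missing it leaves both means, so both describe the same children and the reversal cannot arise. It belongs to the SAP 7.2 tables only.
- **The rule for the geometric mean is inferred.** This stands in part. SAP 7.1 calls it a descriptive statistic and SAP 7.2 gives descriptive statistics the value zero. Since zero is unworkable on the log scale, the inference is strong, but the SAP should say so.
- **The size is unsourced.** This stands. Nothing in the documents supports any particular BQL rate. At an assumed 10% BQL, the truncated-lognormal ratio of geometric to arithmetic mean is 1.01 at log SD 0.5, 0.87 at 0.8 and 0.75 at 1.0, so the reversal is not general at low rates.
- **The data stay visible.** Listings show BQL values, the concentration table's minimum is shown as BQL, and time points with over half BQL are suppressed. This softens the point but does not correct a Ctrough summary from which children are missing. The protocol also defers detail to a separate PK analysis plan, which is not available here and may address the issue.

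**Conclusion.** The concern holds in two limited parts. Under the SAP's own Ctrough definition, a BQL sample 12 hours after the evening dose is removed from a secondary-endpoint summary, which biases both means upward. The arithmetic mean is too high by 7 to 10% at an assumed 10% BQL and by 21 to 34% at an assumed 30%, for lognormal troughs with an assumed log SD of 0.5 to 1.0. In the concentration tables, the two means rest on different children under one n. With a single BQL value the geometric mean exceeds the arithmetic mean when the CV of quantifiable values is below about 66% (n = 6) or 48% (n = 10).

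Two stronger conclusions are not supported. A reader might infer that the rules tilt the trial towards a finding of adequate exposure. The documents set no exposure threshold or adequacy criterion and the analysis is descriptive, so only the direction of the bias can be stated. A reader might also infer that AUC becomes not reportable for children with a BQL value, because SAP 7.3 withholds AUC when a sample is missing from the interval. The SAP does not say whether a BQL value set to missing counts as a missing sample.

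**What to change.** 1. In SAP 7.3, exempt Ctrough from the set-to-missing rule. A BQL trough stays in the Ctrough summary, ranked lowest for the median and minimum and counted as zero in the arithmetic mean as in SAP 7.2, with n BQL shown.
2. Reconcile the SAP and protocol definitions of Ctrough, naming the sample used at each visit.
3. In SAP 7.1 and 7.2, state that the geometric mean and geometric CV use quantifiable values only, and print their own n and n BQL beside the arithmetic statistics.

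Suppressing geometric means, or substituting half the quantitation limit, is not required. The cost is a wording change on data already being collected, one or two extra table rows, and a possibly lower reported Ctrough. Zero understates the mean somewhat, as the working shows, and n BQL lets the reader judge by how much.

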7.3. Blood Pharmacokinetic Parameters

Blood PK parameters for ataluren will be estimated using non-compartmental methods with WinNonlin®. Any data points designated as anomalous values that would impact PK should be predefined before database lock if possible and identified in the report with a rationale for exclusion. The PK parameters will be estimated from the concentration-time profiles, and AUCs will be calculated using the Linear-Log Trapezoidal method (equivalent to the linear up / log down option in WinNonlin). For the estimation of PK parameters, BQL concentration following first dose at pre-dose and up to the first measurable concentration will be set to zero, BQL concentration will be set to missing otherwise. Actual sampling times, rather than scheduled sampling times, will be used in all computations involving sampling times. Actual dose will be used to calculate dose-dependent parameters. Parameters will be summarized by dose (morning, mid-day, evening) and entire day, and visits (baseline, Week 4, and EOT at Week 24). AUC0-tau and AUC0-inf for a subject at any specific dose interval will be reported as NR (not reportable) if there is one sample missing during the dose interval, and consequently the AUC0-24 for the subject at the specified day will be reported as NR.

The following blood PK parameters will be determined using non-compartmental methods as appropriate, for each visit:

Parameter	Description	Dose
C _{max}	Maximum blood concentration; determined directly from the concentration time profile; if the maximum blood concentration occurs at more than one time point, C _{max} is defined as the first maximum value	Morning, Mid- day, Evening
T _{max}	Time to C_{max} ; if the maximum value occurs at more than one time point, T_{max} is defined as the first time point with this value.	Morning, Mid- day, Evening
Ctrough	Trough blood concentration; measured blood concentration at the end of the dosing interval, directly before next administration.	Morning,

Parameter	Description	Dose
AUC ₀₋₂₄	Area under the blood concentration vs time curve (AUC) from time 0 to 24 hours post first morning dose.	Morning
AUC _{0-т}	AUC from time 0 to 6 hours post-dose following the morning and mid-day ataluren doses and AUC from time 0 to 12 hours post- dose following the evening ataluren doses. AUC from time 0 to 6 hours post-dose following the evening ataluren dose will also be calculated.	Morning, Mid- day, Evening
AUC _{0-t}	AUC from time 0 to the last quantifiable blood concentration (C_{last})	Morning, Mid- day, Evening
AUC _{0-inf}	AUC from time 0 to infinity; calculated as $(AUC_{0-T} + C_{last}/\lambda z)$	Morning, Mid- day, Evening
AUC%extrap	Percent of AUC_{0-inf} extrapolated, represented as $(1 - AUC_{0-i}/AUC_{0-inf})^*100$.	Morning, Mid- day, Evening
λz	Apparent first-order terminal elimination rate constant calculated from a semi-log plot of the blood concentration versus time curve. The parameter will be calculated by linear least-squares regression analysis using points in the terminal log-linear phase.	Morning, Mid- day, Evening
T _{1/2}	Apparent first-order terminal half-life; calculated as ln(2)/λz	Morning, Mid- day, Evening
CL/F	Apparent total blood clearance after oral administration; calculated as Dose/AUC _{0-inf}	Morning, Mid- day, Evening
Vz/F	Apparent volume of distribution during terminal elimination phase after oral administration; calculated as $Dose/[\lambda z^* AUC_{0-inf}]$	Morning, Mid- day, Evening
AR _{Cmax}	Accumulation ratio calculated as C _{max} Visit 3 Dose / C _{max} Visit 2 Dose	Morning, Mid- day, Evening
AR _{Cmax}	Accumulation ratio calculated as C _{max} Visit 5 Dose / C _{max} Visit 2 Dose	Morning, Mid- day, Evening
ARAUC	Accumulation ratio calculated as AUC_{0-T} Visit 3 Dose / AUC_{0-T} Visit 2 Dose	Morning, Mid- day, Evening
AR _{AUC}	Accumulation ratio calculated as AUC_{0-T} Visit 5 Dose / AUC_{0-T} Visit 2 Dose	Morning, Mid- day, Evening

Planned dose will be used for the derivation of dose-dependent PK Parameters, planned dose will be determined with use of the PTC124-GD-048-DMD Ataluren Dosing Table (10-, 10-, 20-mg/kg).

In order to estimate the apparent first-order terminal elimination constant, λz , linear regression of concentration in logarithmic scale versus time will be performed using at least three data points spanning 1.5 T_{1/2}. Uniform weighting will be selected to perform the regression analysis to estimate λz . The constant λz will not be assigned if one of the following occurs:

- 1. The terminal elimination phase is not linear (as it appears on a semi-logarithmic scale) as determined by R2adj <0.8.
- 2. The terminal elimination rate constant indicates a positive slope ($\lambda z > 0$).
- 3. T_{max} is one of the three last data points.

Subject experiences vomiting within 3 hours of dose administration will be flagged for the dose period and the day. The PK parameters of the flagged period and day will be excluded from descriptive analysis. Subjects experienced other deviations which may significantly impact PK analysis may be flagged and excluded from descriptive analysis for the specified dose period/day.

No PK parameters will be calculated for subjects with two or fewer detectable concentrations in their PK profile.

No value for λz , AUC_{0-inf}, AUC_{%extrap}, CL/F, Vz/F, or T_{1/2} will be reported for cases that do not exhibit an acceptable terminal log-linear phase in the concentration-time profile.

